12.7.1.4 Graft loss [retransplantation]

A Kaplan-Meier survival probability will be calculated for each regimen. The starting point will be the day of transplant; the end point will be the date of retransplant. Subjects will be censored at date of last follow up if lost to follow up, at date of death, or at study closure (and no longer than 7 years after enrollment). The equality of the two survivor functions will be compared using a rank sum test. Additional models will include adjustment for cluster [site] and receipt of antilymphocyte induction therapy and renal dialysis. The analysis will include assessment of baseline comparability between the two treatment groups. If needed, additional models will be developed to adjust for inequalities not adequately controlled by the randomization process.

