12.7.1.5 Graft loss [death]

A Kaplan-Meier survival probability will be calculated for each regimen. The starting point will be the day of transplant; the end point will be the date of retransplant or date of death if no retransplantation occurs. Subjects will be censored at date of last follow up if lost to follow up, or at study closure (and no longer than 7 years after enrollment). The equality of the two survivor functions will be compared using a Cox model. The survival functions will also be presented adjusted for cluster [site] and stratified by receipt of antilymphocyte induction therapy and renal dialysis. The analysis will include assessment of baseline comparability between the

two treatment groups. If needed, additional models will be developed to adjust for inequalities not adequately controlled by the randomization process

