12.7.1.8 Need for dialysis

Renal failure will be evaluated between the 2 groups using both the ITT and modified ITT populations. Subjects requiring renal replacement therapy [RRT] more than 7 days post-transplant will be considered in the comparison. The proportions of subjects with RRT will be compared stratified by pre-transplant renal status. Timing to start of RRT will also be compared using a Kaplan-Meier probability function.

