12.7.1.9 Post-transplant malignancies

Post-transplant malignancies will be compared in both the ITT and modified ITT populations. The timing to diagnosis will be compared using a Kaplan-Meier probability function and will be stratified by recurrence and new diagnosis. Descriptive statistics will be given on the location/type of malignancy in each study group.

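### Long-term retransplantation is estimated by Kaplan-Meier with deaths censored, and the dialysis and malignancy curves have no stated rule for death, so one minus Kaplan-Meier would not estimate incidence

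*Combined protocol and SAP*

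**What the plan says.** The Protocol Summary lists retransplantation to study closure and post-transplant malignancy as incidences, and RRT as a further exploratory outcome.

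- **Retransplantation (12.7.1.4).** A Kaplan-Meier probability is calculated for each regimen: "The starting point will be the day of transplant; the end point will be the date of retransplant". Death is a censoring event: "Subjects will be censored at date of last follow up if lost to follow up, at date of death, or at study closure". For the comparison: "The equality of the two survivor functions will be compared using a rank sum test".
- **Retransplantation or death (12.7.1.5).** A separate composite counts death: "the end point will be the date of retransplant or date of death if no retransplantation occurs".
- **Dialysis (12.7.1.8).** Crude proportions come first: "The proportions of subjects with RRT will be compared stratified by pre-transplant renal status". Then: "Timing to start of RRT will also be compared using a Kaplan-Meier probability function". No censoring rule is given and death is not mentioned.
- **Malignancy (12.7.1.9).** "The timing to diagnosis will be compared using a Kaplan-Meier probability function and will be stratified by recurrence and new diagnosis". Again there is no censoring rule and no mention of death.

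Section 12 contains no cumulative incidence function or other competing-risk method. Deaths are collected to closure (3.2.3, 7.11) and analysed by arm in 12.7.1.6.

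**The concern.** Kaplan-Meier treats a censored subject as still able to have the event later, at the same rate as those who remain under observation. Section 12.7.1.1 states this assumption for the CMV disease analysis. The check described there and in 12.7.1.6, comparing subjects enrolled early with those enrolled late, deals with staggered entry. It does not deal with death, after which there is no remaining risk of retransplantation, dialysis or malignancy.

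For outcomes labelled as incidence, the natural reading of a reported curve is the share of patients who had the event by a given time. With deaths censored, the curve answers a different question, and its complement is at least as large as that share. Section 4 puts closure 2 years after the last enrolment, following about 3.5 years of accrual, so planned follow-up is roughly 2 to 5.5 years per subject. Section 2.2.2 acknowledges higher mortality in dialysis patients, who are deliberately included. What is at stake is how the long-term exploratory probabilities are described and interpreted.

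**Working it through.** The documents state no long-term rate for RRT, malignancy or death, so there is no plan figure to reproduce. The only relevant event figure is in 6.2.5: fewer than 2% retransplanted after day 30, with no horizon given.

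**Formulas.** Let Le and Ld be constant cause-specific hazards of the event and of death, and T the horizon (5.5 years).

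- One minus Kaplan-Meier with death censored: 1 − exp(−Le·T)
- Cumulative incidence with death competing: Le/(Le + Ld) × [1 − exp(−(Le + Ld)·T)]

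With both cumulative risks fixed, T cancels.

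**One case in full.** One minus Kaplan-Meier 10%, cumulative mortality 20% (assumed). Le·T = −ln 0.9 = 0.1054 and Ld·T = −ln 0.8 = 0.2231, total 0.3285. Cumulative incidence = (0.1054/0.3285) × (1 − 0.9 × 0.8) = 0.3207 × 0.28 = 8.98%. Ratio 10/8.98 = 1.11.

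**Cumulative incidence corresponding to each value of one minus Kaplan-Meier** (mortality assumed):

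| Cumulative mortality | 1−KM 2% | 1−KM 10% | 1−KM 20% | Ratio |
|---|---|---|---|---|
| 10% | 1.90% | 9.50% | 19.02% | 1.05 |
| 20% | 1.79% | 8.98% | 18.00% | 1.11–1.12 |
| 30% | 1.68% | 8.44% | 16.93% | 1.18–1.19 |
| 40% | 1.57% | 7.87% | 15.81% | 1.27–1.28 |

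In points, the overstatement is 0.1 to 0.4 at 2%, 0.5 to 2.1 at 10%, and 1.0 to 4.2 at 20%.

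**Sensitivity to timing.** Putting half of the cumulative death hazard in year 1 gives ratios of 1.07 to 1.39 over the same mortality range. Putting half of the event hazard in year 1 instead gives 1.03 to 1.18.

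**Simulation.** With 88 per arm (176/2), follow-up spread uniformly over 2 to 5.5 years, and 30% mortality at 5 years, mean one minus Kaplan-Meier was 10.0% against a cumulative incidence of 8.5%. At a net risk of 20% the figures were 20.2% against 17.1%. Both agree with the closed form.

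**The case against.** The strongest reply is that these endpoints exist to compare arms, and the comparison is sound. A log-rank or Cox analysis with deaths censored is a valid test of the cause-specific hazard. That stands; only the reported probabilities are at issue.

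A reader might go further and infer that an imbalance in deaths would show up as a false difference in retransplantation, dialysis or malignancy. It would not. Under these constant hazards, the Kaplan-Meier curve with deaths censored depends only on the event hazard among those alive. Take an event hazard of 0.173 over the period in both arms and mortality of 10% and 20%: one minus Kaplan-Meier is 15.9% in both, while cumulative incidence is 15.1% and 14.3%. A Kaplan-Meier gap can be produced by fixing true incidence at 15% in both arms with deaths before the event in 10% and 20%. One minus Kaplan-Meier is then 15.9% and 16.9%. But that set-up forces event hazards of 0.173 and 0.185, a ratio of 1.07, so the gap reflects a real difference in the cause-specific hazard. Mortality moves cumulative incidence, which is why the two quantities need to be read together.

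Other objections also limit the point:

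- **Retransplantation is rare.** Two percent of 88 is about two subjects per arm.
- **The bias is small against sampling error.** At 15% and 88 per arm the standard error is √(0.15 × 0.85/88) = 3.8 points. The overstatement there, with 10% to 30% dying before the event, is 0.9 to 3.1 points. The bias is systematic, but it would not dominate.
- **Partial safeguards exist.** The crude RRT proportions do not have this bias, although they ignore unequal follow-up. The composite in 12.7.1.5 handles death for retransplantation, and 12.7.1.6 shows deaths by arm. Malignancy has no comparable analysis.
- **RRT and malignancy are conditional.** Those sections speak of timing and give no censoring rule. It would go too far to say that they specify a biased estimate; the overstatement follows only if deaths are censored by default.
- **No mortality rate is stated.** Section 2.2.2 says that mortality is higher in dialysis patients and that first-year deaths were considered in the sample size. It does not support any particular long-term figure.

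**Conclusion.** The point holds as a minor one about reporting. In 12.7.1.4 the plan chooses an estimator whose complement is not the incidence that the endpoint names; in 12.7.1.8 and 12.7.1.9 it leaves the handling of death open. The relative overstatement is about 5% to 27% for assumed cumulative mortality of 10% to 40% with constant hazards, and ranges from 3% to 39% when deaths or events are concentrated early. In absolute terms it is a few tenths of a point for retransplantation after day 30, and reaches 1 to 4 points only if RRT or malignancy is around 20%. All mortality rates, and all event rates other than the 2%, are assumptions. Valid cause-specific comparisons, the primary and secondary analyses and the sample size are unaffected.

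**What to change.** In 12.7.1.4, 12.7.1.8 and 12.7.1.9:

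1. State explicitly how death is handled in each time-to-event analysis.
2. Report Aalen-Johansen cumulative incidence by arm, with confidence intervals, at annual points, with death as a competing event.
3. Keep a cause-specific log-rank or Cox test for the comparison, and name it in 12.7.1.8 and 12.7.1.9, where the Kaplan-Meier comparison currently has no named test.
4. Interpret both quantities alongside mortality by arm from 12.7.1.6.

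This changes analysis wording only. Deaths are already collected to closure, so no new data, subjects or procedures are needed, and the output is standard in SAS or Stata. The cost is having two quantities to explain, cumulative incidence and cause-specific hazard, which can differ between arms in different ways.

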12.7.1.5 Graft loss [death]

A Kaplan-Meier survival probability will be calculated for each regimen. The starting point will be the day of transplant; the end point will be the date of retransplant or date of death if no retransplantation occurs. Subjects will be censored at date of last follow up if lost to follow up, or at study closure (and no longer than 7 years after enrollment). The equality of the two survivor functions will be compared using a Cox model. The survival functions will also be presented adjusted for cluster [site] and stratified by receipt of antilymphocyte induction therapy and renal dialysis. The analysis will include assessment of baseline comparability between the

two treatment groups. If needed, additional models will be developed to adjust for inequalities not adequately controlled by the randomization process

12.7.1.6 All-cause mortality

A Kaplan-Meier survival probability will be calculated for each regimen. The starting point will be the date of randomization and the end point will be date of death. Subjects will be censored at date of last follow up if lost to follow up, or at study closure (and no longer than 7 years after enrollment). The equality of the two survivor functions will be compared using a rank sum test for both the non-stratified data as well as the stratified log rank test for each stratum separately (receipt of lymphocyte depleting induction therapy and renal dialysis). The number of subjects available at annual time points will be reported, along with the Kaplan-Meier probability and associated 95% confidence intervals. To validate the assumption of that all subjects have similar probability of survival at each time point despite different follow up, relevant baseline characteristics will be compared between subjects enrolled in the first half of the study with those enrolled later. If the 2 cohorts are similar, we can expect that the survival probabilities are valid irrespective of variable follow up. Survival will also be examined between the two cohorts.

12.7.1.7 Opportunistic infections

Incidence rates [number of infections per patient days of follow up] will be calculated. Patient days will be counted from the day of randomization until the date of death, end of study or last known follow up if subject is lost to follow up. The rates will be compared between the two groups using both the ITT population and modified ITT populations. The incidence rate will be calculated for all OI combined. Separate rates will also be calculated for bacterial and fungal infections. Similar analyses will be done using the date of study closure as the endpoint.

12.7.1.8 Need for dialysis

Renal failure will be evaluated between the 2 groups using both the ITT and modified ITT populations. Subjects requiring renal replacement therapy [RRT] more than 7 days post-transplant will be considered in the comparison. The proportions of subjects with RRT will be compared stratified by pre-transplant renal status. Timing to start of RRT will also be compared using a Kaplan-Meier probability function.

12.7.1.9 Post-transplant malignancies

Post-transplant malignancies will be compared in both the ITT and modified ITT populations. The timing to diagnosis will be compared using a Kaplan-Meier probability function and will be stratified by recurrence and new diagnosis. Descriptive statistics will be given on the location/type of malignancy in each study group.

12.7.2 Use of hematopoietic growth factors

12.7.2.1 Frequency of use

The number and percentage of subjects in the modified ITT population receiving any hematopoietic growth factor (e.g., G-CSF) during the study treatment period will be tabulated, by study group. The study groups will be compared using a CMH test of the odds ratio controlling for anti-lymphocyte induction and renal dialysis.

12.7.2.2 Number of dosages

Total doses of will be compared between the study groups using a Mann Whitney test. Time to use of G-CSF will also be evaluated with the starting point as date of randomization and the end point date of use of G-CSF. A rank sum test will be used to compare the two groups. Summary tables will be presented with descriptive statistics for percent use, timing and total dosage of G-CSF for each group.

12.7.3 Immunologic endpoints [CMV-specific immunity]

12.7.3.1 T-cell immunity

Initial sample [100 days]: The proportions of subjects with detectable CMV specific monofunctional CD4+ and CD8+ T-cells (that produce IFN- γ) and CMV-specific multifunctional CD4+ and CD8+ T-cells (≥ 2 markers that include IFN- γ + additional cytokines such as IL-2 and TNF- α) will be compared between the two groups. It is hypothesized that T-cell immune responses will be greater in preemptive versus prophylaxis group and that positive responses will correlate with lack of development of CMV disease overall and late-onset CMV disease (69). A number of analyses will be carried out for these assessments. Proposed threshold levels that confer protection against CMV in transplant recipients are 0.4 CMV-specific T-cells/ μ l for both CD4+ and CD8+ T-cells (69). The percent of responders will be compared between the two treatment regimens using a Mann Whitney test.

The mean, median, range of multifunctional CD4+ and CD8+ T-cells will be summarized between the two regimens. The rate of CMV positive responders and the absolute number of CMV-specific T-cells will be compared between the subjects with adjudicated CMV disease and those without disease using GEE models. A receiver operator characteristic (ROC) will be used to estimate a cutoff for number of CMV-specific T-cells that appear to prevent the development of CMV disease.

Follow up samples [6 and 12 months] for immune assays will also be evaluated as above. In addition, a repeated measures model will be used to evaluate the relationship of each type of CMV response over time and the development of CMV disease.

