These results suggest greater development of CMV-specific T-cell responses with preemptive therapy compared to prophylaxis. And similar to data from other studies summarized above, the incidence of late-onset of CMV disease in this cohort was significantly higher in the prophylaxis compared to preemptive therapy group (10/29 [34%] vs. 0/19 [0%]), respectively, $p=0.0035$. Multifunctional T cells were more common among subjects without CMV disease (Figure 2). However, since this was not a randomized controlled study, potential confounders (induction vs. no induction immunosuppression, intensity of maintenance immunosuppression etc.) might also explain, at least in part, these apparent differences, and thus there is a need to assess these parameters more definitively in the context of a randomized controlled trial.

[figure not shown]
We will conduct immunologic testing for CMV-specific T-cell and neutralizing antibodies (UL128-131 epithelial/endothelial targets) in the study subjects. Previous studies have considered transplant patients with ≥ 0.4 CMV-specific CD4+ and CD8+ T-cells/ μ L as responders (45). Our study will assess differences in T-cell and antibody-mediated responses in the 2 groups and determine thresholds that confer protection against CMV disease.

Prophylaxis is considered to have a greater salutary effect on CMV-related indirect outcomes (46). However, this has not been incontrovertibly shown in liver transplant recipients. In a randomized, placebo-controlled trial, no difference in rejection, graft loss or mortality at 12 months was observed with the use of oral ganciclovir prophylaxis versus placebo (8). Studies comparing ganciclovir with other agents e.g., acyclovir have yielded similar results (47). A report of the Collaborative Transplant Study which is a large database from 435 transplant centers in 44 countries concluded that unlike other organ transplant recipients, CMV prophylaxis had no significant impact on the rate of acute rejection or graft survival in liver transplant recipients (48). There is also evidence that all outcomes with the use of preemptive therapy in liver transplant recipients are comparable to those in patients who never developed CMV infection (22).

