5.4.2 Randomization

Subjects will be randomized in 1:1 allocation to one of 2 study groups. All subjects that have met all criteria for study enrollment and have given written informed consent will be randomized via a web-based randomization system at the study web-portal.

The study team member randomizing the subject will get an immediate message providing group assignment. Randomization at each site will be stratified by: 1) the receipt of lymphocyte depleting induction and 2) dialysis at time of randomization. Randomization will occur as soon as it is feasible, but no later than 10 days after transplantation. Inadvertently randomized

subjects who do not meet the inclusion/exclusion criteria or those who are withdrawn prior to receiving the study drug will be replaced.

Subjects receiving lymphocyte depleting induction at the time of transplantation (even for those randomized to the preemptive therapy group) may receive up to 10 days of antiviral therapy with valganciclovir or IV ganciclovir after transplantation. Additionally, if the treating physician prescribes valganciclovir or IV ganciclovir for any length of time prior to randomization, it will not preclude subject enrollment. For subjects assigned to the prophylaxis group, the first dose of study drug should be given on the day of randomization regardless of lymphocyte induction. For subjects in the preemptive group that have received lymphocyte depleting induction, antiviral therapy with valganciclovir or IV ganciclovir will be given for ten days then stopped. Subjects that have not received lymphocyte depleting induction, but have received doses of valganciclovir or IV ganciclovir after transplantation prior to randomization, will have the pre-randomization treatment stopped and begin study treatment on randomization day based on their assigned group.

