12 STATISTICAL CONSIDERATIONS

12.1 Sample size calculations

The primary endpoint is the incidence of CMV disease within 12 months post transplantation. The null hypothesis is that the incidence of CMV disease in the prophylaxis group is equal to that in the preemptive therapy group. The null hypothesis will be rejected if there is a significant difference between the two groups at 0.05. The sample size estimates have been calculated based on the numbers required to detect a disparity in two survivor functions using a two-sided log-rank test [stpower logrank, STATA version 10.1]. The calculations are based on a realistic and conservative expectation in differences in event (CMV disease), feasibility and clinically relevant effect size. The mean CMV disease rate (weighted for study size) for prophylaxis and preemptive therapy studies (depicted in the Tables in the Background section of the protocol) is 30.6% (95% CI 24.1-37.1) and 0.78% (95% CI: 0-2.4%), respectively. Based on power calculations that coincide with the lowest observed rate for CMV disease in prophylaxis studies and highest rate observed in preemptive therapy studies, we assume that CMV disease will occur in 20% of the subjects in the prophylaxis and 5% in the preemptive therapy group. A sample size of 160 study subjects (80 per group) will detect this difference with power of 80% and alpha =0.05 using two-sided Fisher's exact test for two independent proportions. The Table below provides sample size estimates for CMV disease rates of 20-25% in the prophylaxis and 5-7% in the preemptive therapy group.

Prophylaxis group		Preemptive therapy group		Hazard ratio	Power	Estimated events	Sample size each group	Total sample
Estimated disease rate	Disease free survival	Estimated disease rate	Disease free survival					
25%	.75	7.1%	.929	.254	.83	25	75	150
25%	.75	7.1%	.929	.257	.85	26	80	160
22%	.78	7.0%	.930	.291	.80	27	90	180
20%	.80	5.0%	.950	.229	.80	20	80	160
20%	.80	6.0%	.941	.273	.80	25	93	186
20%	.80	5.4%	.946	.247	.80	22	85	170
20%	.80	7.0%	.930	.325	.80	31	112	224

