12.4 Data Analyses

12.4.1 General considerations

All statistical analyses will be performed using STATA version 10.1 or later [Stata Corp, College Station, TX] or SAS version 9.2 or later [SAS Institute Inc., Cary, NC]. Cost efficacy analysis will use TreeAge Pro 2011 or later [TreeAge software, Williamstown, MA]. Tests of statistical significance will be two sided at an alpha of 0.05 unless otherwise specified.

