12.7.3.2 Neutralization antibody

This will be measured as titer of CMV neutralizing antibody [dilution factor]. Currently, the precise relationship between CMV neutralizing antibody and CMV disease is uncertain, therefore a number of exploratory analyses will be performed.

Initial sample [100 days]: The percent of samples demonstrating any detectable CMV neutralizing antibody will be compared between the two groups using a Chi square test. This activity will also be quantitatively evaluated. The titers will be transformed to a log10 and the log mean titers will be compared between the two groups using a t-test. A generalized estimating equation [GEE] regression model will be used to examine the relationship of antibody to CMV disease. The log transformed levels will be compared between a dichotomized grouping [subjects that develop CMV disease and those that remain disease free] using a t-test. The timing to onset of late CMV disease will also be compared between subjects with and without CMV antibody activity using a Kaplan-Meier probability estimate. The two probability functions will be compared using a rank sum test.

Follow up samples [6 and 12 months]: The follow up samples will be evaluated similarly to the initial sample. In addition, the log difference between the initial sample and the follow up sample will be calculated and compared between the two regimens using a regression analysis. A repeated measures model will be used to evaluate the relationship of CMV antibody activity over time and the development of CMV disease.

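### The immunity-to-disease analyses name neither arm nor induction, and those that cannot carry arm (t-test, rank sum test, single ROC cutoff) pool the two arms, so a protective association or cutoff can arise from the arm difference alone

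*Combined protocol and SAP*

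**What the plan says.** For T-cells (Section 12.7.3.1), the arms are compared first: "The percent of responders will be compared between the two treatment regimens using a Mann Whitney test". Responder rates and absolute counts are then related to disease: they "will be compared between the subjects with adjudicated CMV disease and those without disease using GEE models". One ROC analysis gives a count above which disease appears to be prevented. The 6- and 12-month samples are handled in the same way, with a repeated-measures model added.

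For neutralizing antibody (Section 12.7.3.2), the arms are compared by chi-square for any detectable antibody, and "the log mean titers will be compared between the two groups using a t-test". Antibody is related to disease by a GEE model, by a t-test of log titer between subjects with and without disease, and by Kaplan-Meier curves for late disease compared with a rank sum test. Follow-up samples add a regression between arms and a repeated-measures model.

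Neither section names arm, induction or dialysis as a covariate or stratum. Section 12.4.1 has no general adjustment rule; on testing it says only "Tests of statistical significance will be two sided at an alpha of 0.05 unless otherwise specified". Randomization is "stratified by: 1) the receipt of lymphocyte depleting induction and 2) dialysis at time of randomization" (Section 5.4.2), and most other endpoint sections write out control for induction and usually dialysis, including the exploratory growth-factor endpoint in Section 12.7.2.1.

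**The concern.** Two kinds of comparison sit in Section 12.7.3. The comparison of arms is randomized. The comparison of diseased with disease-free subjects is not, and randomization does not protect it.

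By the plan's own assumptions arm drives both sides of that second comparison. Section 12.7.3.1 hypothesises greater T-cell responses with preemptive therapy, and for disease Section 12.1 says "we assume that CMV disease will occur in 20% of the subjects in the prophylaxis and 5% in the preemptive therapy group". Responders will then come mostly from the preemptive arm and cases mostly from the prophylaxis arm. A pooled analysis shows fewer cases among responders even if T-cell response tells nothing about disease within either arm. Section 2.2 also gives arm a route to T-cells that need not involve protection: ganciclovir itself suppresses T-cell proliferation. The first immune sample is at day 98 ± 14, when prophylaxis subjects are still on, or have only recently stopped, a 100-day course.

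At stake is the aim in Section 2.2.1 of finding immune thresholds that protect against CMV disease. The pooled analysis could appear to confirm the mechanism, and supply a cutoff, when the data show only that the two strategies differ in both quantities.

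**Working it through.** **Inputs.** Disease 20% prophylaxis, 5% preemptive, 80 per arm, two-sided alpha 0.05 (Sections 12.1, 12.4.1). T-cell responders 8/15 (53%) preemptive, 3/19 (16%) prophylaxis (Table 1, Section 2.2.1: CD8 IFN-γ response to pp65). Alternative disease rates: literature 30.6% vs 0.78% (Section 12.1); pilot late-onset 10/29 (34%) vs 0/19 (Section 2.2.1).

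**The plan's own figures.** Section 12.1 states: "A sample size of 160 study subjects (80 per group) will detect this difference with power of 80% and alpha =0.05". Exact enumeration of the two-sided Fisher test gives 79.3%, so the figure reproduces. Fisher tests on the pilot counts give p = 0.030 (8/15 vs 3/19) and p = 0.0035 (10/29 vs 0/19), matching the stated 0.03 and 0.0035. Section 12.7.3 states no sample size or power.

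**Pooled association with none within arm.** Let r be the responder proportion and d the disease risk, independent within each arm (E preemptive, P prophylaxis), n = 80 per arm.

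- Responders: n(rE + rP) = 80 × (0.53 + 0.16) = 55.2. Cases among them: n(rE·dE + rP·dP) = 80 × (0.53 × 0.05 + 0.16 × 0.20) = 80 × 0.0585 = 4.68. Risk 4.68/55.2 = 8.5%.
- Non-responders: 160 − 55.2 = 104.8. Expected cases in all: 80 × (0.05 + 0.20) = 20, so 20 − 4.68 = 15.32. Risk 15.32/104.8 = 14.6%.
- Odds ratio: (4.68/50.52) / (15.32/89.48) = 0.0926/0.1712 = 0.54.

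The true odds ratio within each arm is 1.

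**False rejection.** Trials were simulated under the same independence, with a pooled 2×2 chi-square test and a Mantel-Haenszel test stratified by arm. The 2×2 test stands in for an unadjusted model with one record per subject. Ranges reflect rounded (53%, 16%) or exact (8/15, 3/19) pilot proportions.

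| Disease, prophylaxis / preemptive | Responders, preemptive / prophylaxis | Pooled OR | Pooled test rejects | Stratified by arm |
|---|---|---|---|---|
| 20% / 5% (design) | 53% / 16% | 0.54 | 18–19% | about 5% |
| 30.6% / 0.78% (literature) | 53% / 16% | 0.33–0.34 | 55–56% | about 5% |
| 34% / 0% (pilot) | 53% / 16% | 0.30–0.31 | 64–66% | about 5% |
| 20% / 5% | 35% / 25% (assumed) | 0.85 | about 5% | about 5% |
| 20% / 20% (assumed equal) | 53% / 16% | 1.0 | about 5% | about 5% |

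**ROC.** Take log counts as normal with equal spread and an arm shift of 1.09 SD, the shift implied by 53% vs 16% responders. The pooled area under the curve is then 0.60, 0.66 and 0.67 in the first three scenarios, from arm alone.

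**Induction.** The documents give no figures. With assumed prevalence 10–40%, disease risk ratio 1.5–3 and responder ratio 0.5–0.7, the residual within-arm odds ratio is 0.69–0.98. Over most of that range this is a smaller distortion than that from arm.

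**Events by arm.** At the design rates, 0.20 × 80 = 16 cases in prophylaxis and 0.05 × 80 = 4 in preemptive. The chance of three or fewer in the preemptive arm is 43%.

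**The case against.** **The plan is silent, not wrong.** A GEE, regression or repeated-measures model can carry arm and induction, and both sections announce a number of analyses. A reader might infer that the plan specifies unadjusted models; it does not, it leaves the covariates open. This stands for the models. It does not help the t-test by disease status, the rank sum test or the single ROC, which as written have no place for arm.

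**Omitting induction does not bias the comparison of arms.** This stands in full. A reader might infer bias from Section 2.2.1, which says that "potential confounders (induction vs. no induction immunosuppression, intensity of maintenance immunosuppression etc.) might also explain" the differences seen. That sentence is about the non-randomized pilot and gives this as the reason for a randomized trial. Allocation here is stratified on induction, so leaving it out of the between-arm tests costs only precision. The amount cannot be read from the documents: a rise in power from 80% to 84–90% needs an assumed 10–25% of variance explained by induction and a base power that Section 12.7.3 does not state.

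**Immunity may lie on the path from arm to disease.** If preemptive therapy protects through T-cells, conditioning on arm discards the between-arm part of the association. This stands as a reason to report pooled and arm-adjusted results together. It does not rescue a pooled result on its own: if T-cells protect, an association should also exist within arm, and the pooled figure cannot show whether it does.

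**Within-arm evidence will be thin.** This also stands. At the design rates the arm-stratified test has about 14% power for a true within-arm odds ratio of 0.5, and 34% for 0.3. With no preemptive cases, as in the pilot, that arm yields no estimate. A rule that accepts a threshold only if it holds within each arm would usually miss a real association.

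**Conclusion.** The concern holds for the analyses that relate immunity to disease. Followed as written, they can return a protective association and cutoff produced entirely by the arm difference: odds ratio 0.54 with about 18% false rejection at the design rates, and 55% or 64% with the literature or pilot disease rates, against about 5% when stratified by arm.

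The size rests on both arm differences being real. The responder proportions come from 15 and 19 non-randomized patients. If the arms differ little in response or in disease, the problem all but disappears.

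The documents do not support extending this to the randomized comparison of immune response between arms, where the omitted strata are a matter of precision and of consistency with the other endpoints. Nor do they support extending it to the trial's main conclusions: these are exploratory endpoints, and the primary result does not depend on them.

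**What to change.** In Sections 12.7.3.1 and 12.7.3.2:

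1. Include arm, induction and dialysis in the GEE and repeated-measures models of immunity and CMV disease.
2. Replace or supplement the t-test by disease status and the rank sum test with versions stratified by arm.
3. Report the ROC cutoff adjusted for arm, or estimated in the prophylaxis arm where most events are expected, beside the pooled cutoff.
4. Describe any association or cutoff seen only in the pooled analysis as not separable from the difference between arms.
5. State in advance that the preemptive-arm estimate will be very imprecise (about 4 expected events) and may not be estimable. Do not require significance within each arm.

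Separately, for precision and consistency, use the randomization strata in the between-arm comparisons: a CMH test for responder proportions, a van Elteren test for counts, and linear regression of log10 titer on arm, induction and dialysis.

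The cost is SAP wording. All the variables are already collected, and no visit, sample or sample size changes. The price is a wider interval on the arm-adjusted immunity-to-disease association, which reflects what the trial can show about it.
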